Our specific aim is to conduct a pilot study to evaluate the accuracy of continuous glucose monitors (CGM) in End Stage Renal Disease (ESRD) patients on intermittent hemodialysis (iHD). Accuracy will be assessed by calculating the mean absolute relative difference (MARD) between CGM values and concurrent finger stick or venous blood glucose (CBG) in these patients during hemodialysis, and on non-dialysis days.

Primary Hypotheses: The MARD between CGM sensor glucose and CBG will be larger on non-HD days than during dialysis.

Study Design: Biomedical

1. Will controls be used?

Yes – patients are their own controls.

▶ **IF YES, explain the kind of controls to be used.**

Accuracy of CGM during HD session will be compared to the accuracy of the CGM on the same patient when they are not in HD session.

2. What is the study design?

Prospective cohort study using blinded 10-day CGM in 30 ESRD patients on iHD who have a diagnosis of type 1 diabetes mellitus or type 2 diabetes mellitus. Will attempt to recruit approximately 15 participants who use insulin therapy though this is not exclusionary. Patients will be requested to perform finger stick blood glucose (FSBG) values using a study glucometer 7 times daily at home (before meals, 2 hours after meals, and at bedtime) for 10 days. A study team member will obtain approximately 12 blood samples from the existing HD IV line during each (three) HD session the CGM sensor is worn. These blood samples will be immediately processed using the *i-STAT System*. While the goal is to have the subject participate in three hemodialysis sessions, two sessions will be acceptable and not considered a study deviation.

3. Does the study involve a placebo?

No

▶ **IF YES, provide a justification for the use of a placebo**

Human Participants

Ages: 18+

Sex: Any

Race: Any

Subjects- see below

1. Provide target # of subjects (at all sites) needed to complete protocol.

30 subjects

2. Describe expected rate of screen failure/ dropouts/withdrawals from all sites.

40%

3. How many subjects will be enrolled at all sites?

Up to 50 subjects

4. How many subjects will sign a consent form under this UVa protocol?

Up to 50 subjects.

Inclusion/Exclusion Criteria

1. List the criteria for inclusion

- Ages 18+
- Type 1 diabetes mellitus on intermittent HD thrice weekly OR Type 2 diabetes mellitus on intermittent HD thrice weekly
- Willingness and ability to comply with scheduled visits and study procedures

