2. List the criteria for exclusion

- Noncompliant with HD therapies
- Pregnant women
- Subjects with Hct < 30. This will be determined via the monthly blood draw that the subjects coordinate with entry into the study.

3. List any restrictions on use of other drugs or treatments.

- Hydroxyurea - has been known to interfere with current continuous glucose monitor sensors.

Statistical Considerations

1. Is stratification/randomization involved?

No

► IF YES, describe the stratification/ randomization scheme.

► IF YES, who will generate the randomization scheme?

_____ Sponsor

_____ UVa Statistician. Answer/Response:

_____ UVa Investigational Drug Service (IDS)

_____ Other: Answer/Response:

2. What are the statistical considerations for the protocol?

This is a prospective cohort study of 30 patients with diagnosis of Type 1 or Type 2 diabetes mellitus. The patients enrolled in the study will have a blinded CGM placed for 10 days which will measure interstitial glucose using above referenced electroenzymatic technology and record interstitial blood glucose every 5 minutes. The CGM sensor will be collected 10 days after placement of the sensor. The patients will also check venous blood glucose using a provided glucometer seven times daily on non-HD days. During HD sessions, a study team member will measure blood glucose with the use of an *i-STAT System* point of care machine approximately 10-12 times at the following intervals: q15 minutes x 90 minutes, q30 minutes x 60 minutes, then q60 minutes until HD finished. The results from the *i-STAT System* glucose measurements will be recorded in the study flowsheet. The study glucometers will record and store the results of finger stick blood glucose values which will be collected each day (10 days) after placement of the

sensor. The CGM sensors may be discarded by the study subject. CGM transmitters will be returned to the study team. .

The CGM and study glucometer data will be compared in the 30 patients to assess accuracy in between hemodialysis sessions (HD day + 1 [considered euvoletic] and HD day + 2 day [considered volume overloaded]). MARD will be calculated.

3. Provide a justification for the sample size used in this protocol.

This is a small pilot study to assess MARD (accuracy) of CGM in hemodialysis dependent patients with diabetes.

4. What is your plan for primary variable analysis?

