Data scientists at the center for diabetes technology will use CGM, glucometer, and iStat data to calculate the MARD between sensor glucose and venous blood glucose for patients during hemodialysis, and between hemodialysis in different volume states.

5. What is your plan for secondary variable analysis?

Secondary outcomes include duration of HD, volume removed during HD therapy, Basic Metabolic Panel (BMP) prior to HD session including Co2, BUN, glucose, complete blood counts, medications, and daily weight.

6. Have you been working with a statistician in designing this protocol?

No

IF YES, what is their name?

7. Will data from multiple sites be combined during analysis?

No. , Only UVA patients will participate in this study.

7(a). Does the study involve randomization?

IF YES, will randomization be done at each site or among sites?

7(b). Has the sample size calculation considered the variation among sites?

7(c). When combining the data from multiple sites to assess the study results, is the effect of the treatment to be tested (or the association to be tested) assumed to be the same across sites or vary among sites? What is the modelling strategy?

7(d). Is there a common protocol used in all sites?

Study Procedures-Biomedical Research

1. What will be done in this protocol?

Screening (Visit 1):

Potential subjects will be approached during their regularly scheduled dialysis sessions at a UVA dialysis facility. Subjects may be contacted via telephone as well. The subject's provider or study

physician may introduce the study to the potential subject. If interested, a member of the study team will discuss the study in detail and obtain informed consent. Pre-screening inclusion/exclusion questions regarding their possible eligibility for the trial may be reviewed.

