Upon consent, the study team member will review the subject's inclusion/exclusion criteria will be assessed by the study team to ensure criteria has been met. The study team member will review the subject's medical history and medications. A serum pregnancy test will be performed for women who are of child-bearing potential. If a subject is pregnant, they will be withdrawn from the study and be advised to seek further confirmation from their primary provider. If the subject meets all criteria, they may continue with the CGM training visit on the same day or at a later date. Fingertick and *i-STAT System* blood glucose values are for study purposes only. Treatment recommendations will not be provided.

The most recent Hemoglobin A1c value that is collected for standard of care and is either dated prior to the study start date or within the data collection period if the duration between the collection date and study start date is greater than 3 months.

Day 1 (Visit 2):

Day 1 may occur on the same day as Screening. At the end of the subject's dialysis session, the study team will insert a DexCom G6 CGM sensor into the participant's abdomen and educate the subject on the use of the DexCom G6 CGM. The CGM will be blinded to both the study physician and participant during the course of study participation – there will be no visible readings during the subject's participation in the study. Selected study team members may incidentally see sensor values when downloading the CGM data. CGM supplies and CGM user's guide will be provided to the participant. Patients will be given a study glucometer, testing supplies, and a scale to measure body weight each day. They will be taught how to use the study glucometer and informed of the schedule for fingerstick monitoring that will occur during the 10 days of wearing the CGM. Subjects will also be asked to weigh themselves every morning with the study-supplied scale and record it in a study record.

Non-Dialysis Days (Days 2, 3, 7, 9, 10):

On days that the subject does not have dialysis, they will perform 7 fingerstick blood glucose tests using the study glucometer. These will be done before meals, after meals, and at bedtime. Subjects will be encouraged to use the study glucometer for any additional blood glucose values they wish to perform.

Subjects will weigh themselves every morning upon voiding and record the results in a study record.

Dialysis Days (Days 4, 6, 8, 11):

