On days that the subject has dialysis, they will attend their regularly scheduled dialysis session and perform that run with no change from standard care. During the session, 10-12 samples (1.5

cc) of blood will be drawn from the HD line that is placed for usual care purposes. These samples will occur at approximately the following times:

0m, 15m, 30m, 45m, 60m, 75m, 90m, 120m, 150m, 210m, then every 60 minutes until the end of the dialysis session.

The blood samples will be used to perform a blood glucose test using an *i-Stat System*. The study team will record results and data obtained clinically for the subjects during this time including lab results (e.g. weekly basic metabolic panel, etc...), dialysis run information (including dextrose concentration of the dialysate), vital signs including height and weight, and other clinically relevant medical information. Estimated blood loss will be 20cc per HD session and 60cc per study period. Glucose values collected during the dialysis session will not be used for treatment purposes.

At Home:

Participants will perform 7 fingerstick blood glucose tests using the study glucometer. These will be done before meals, after meals, and at bedtime. Subjects will be encouraged to use the study glucometer for any additional blood glucose values they wish to perform.

Subjects will weigh themselves every morning upon voiding and record the results in a study record.

While the goal is to have the subject participate in three hemodialysis sessions, two sessions will be acceptable and not considered a study deviation.

Final Study Visit (Day 11)

At the final study visit, subjects will remove the CGM sensor from their abdomen. The sensor will be discarded. The CGM transmitter will be returned to the study team. They will discontinue all use of other study equipment (e.g. study glucometer, scale, etc...) and return all study supplies to the study team. Subjects will continue with their standard care for their end-stage renal disease and diabetes management.

The CGM equipment stores the blood glucose values on the transmitter. The study glucometer will be downloaded by study staff once the subject returns the equipment to the team.

Weigh diaries will be completed.

HSR190012: Evaluation of accuracy of continuous glucose monitoring (CGM) in patients with end stage renal disease (ESRD) on intermittent hemodialysis (iHD).

Fingerstick Schedule for Monday, Wednesday, Friday dialysis patients

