Dialysis day. Place CGM sensor. Check FSBG before meals and at bedtime.	7 FSBG readings: before & after meals & at bedtime.	7 FSBG readings: before & after meals & at bedtime.	Dialysis day. Obtain 10-12 iStat glucose values during HD session: q15m x 90min, q30m x 60min, q60m until end of HD session; 7 FSBG readings: before & after meals & at bedtime	7 FSBG readings: before & after meals & at bedtime.	Dialysis day. Obtain 10-12 iStat glucose values during HD session: q15m x 90min, q30m x 60min, q60m until end of HD session; 7 FSBG readings: before & after meals & at bedtime	7 FSBG readings: before & after meals & at bedtime.	Dialysis day. Obtain 10-12 iStat glucose values during HD session: q15m x 90min, q30m x 60min, q60m until end of HD session; 7 FSBG readings: before & after meals & at bedtime	7 FSBG readings: before & after meals & at bedtime.	7 FSBG readings: before & after meals & at bedtime.	Dialysis day. Final study visit to return study supplies. No FSBGs.

2. If this protocol involves study treatment, explain how a subject will be transitioned from study treatment when they have completed their participation in the study.

This is not a treatment study. Subjects will discontinue use of study equipment and return all supplies to the study team. Subjects will continue with their usual care and management of their diabetes and end-stage renal disease.

Subject Compliance with Study Procedures

1. Explain how the study team will monitor the subject for compliance with the study procedures.

Research coordinator will check in with patient at each HD session (3 sessions) during study period to review protocol and assess compliance.

2. Describe criteria for when a subject is considered to be non-compliant with study procedures.

If patient obtains <3 finger sticks per day, or misses one HD session, the patient will be considered non-compliant.

Bibliography

2. Berg, E.G. (2014, May). Anatomy of a CGM Sensor. Retrieved February, 2019, from <http://www.diabetesforecast.org/2014/05-may/anatomy-of-a-cgm-sensor.html>
3. Tkattula. (2018, April 11). Safety Information. Retrieved February, 2019, from <https://www.dexcom.com/safety-information#dexcom-g6-brief>

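### Does failing to separate a skipped dialysis session from an unsampled one undermine the comparison of CGM accuracy by volume state?

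*Combined protocol and SAP*

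**What the plan says.** Three places deal with missed sessions.

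- Subject Compliance with Study Procedures, item 2: "If patient obtains <3 finger sticks per day, or misses one HD session, the patient will be considered non-compliant". No consequence for the analysis is attached.
- Study Design, item 2, repeated in Study Procedures under At Home: "While the goal is to have the subject participate in three hemodialysis sessions, two sessions will be acceptable and not considered a study deviation".
- Subject Compliance, item 1: "Research coordinator will check in with patient at each HD session (3 sessions) during study period to review protocol and assess compliance".

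Two places define the analysis that could be affected. Statistical Considerations, item 2, assesses accuracy between sessions in two states, "HD day + 1 [considered euvoletic] and HD day + 2 day [considered volume overloaded". Item 4, the primary variable analysis, calculates the mean absolute relative difference (MARD) "for patients during hemodialysis, and between hemodialysis in different volume states". The primary hypothesis, under Objectives/Hypothesis, is a different contrast: non-dialysis days against dialysis.

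**The concern.** A subject with two of the three sessions appears to be acceptable under one rule and non-compliant under another. The two rules use different verbs (*participate* and *misses*), and neither is defined.

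The ambiguity could reach the analysis because the two possible events differ. If dialysis went ahead but no samples were drawn, only in-session pairs are lost, and every later day keeps its volume state. If dialysis was skipped, the same pairs are lost and later days also lie further from the last dialysis. The plan has no class beyond the second day after dialysis and does not say what happens after a skip. If an analyst labelled days from the schedule table, readings three or four days after dialysis would enter the group regarded as euvolemic and blur the contrast between volume states. If the analyst labelled from the last completed dialysis, those readings would have no class, and someone would have to decide what to do with them after the data are in.

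**Working it through.** **Inputs.** The fingerstick schedule tables for both dialysis patterns give dialysis on Days 1, 4, 6, 8 and 11, and 7 fingersticks on each of Days 2 to 10. The non-dialysis heading in Study Procedures omits Day 5, but both tables show it as a non-dialysis day, so the tables are used. The target is 30 completing subjects. I assume no make-up session and that all scheduled fingersticks are taken.

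**The plan's own count.** The procedures heading reads "Dialysis Days (Days 4, 6, 8, 11". The tables make Day 11 the final visit with no sampling, which leaves Days 4, 6 and 8. That is three sampled sessions, in agreement with "obtain approximately 12 blood samples from the existing HD IV line during each (three) HD session the CGM sensor is worn" in Study Design, item 2.

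**Schedule kept.** Days since dialysis = day number minus the last dialysis day.

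- +1: Days 2, 5, 7, 9, so 4 × 7 = 28 readings.
- +2: Days 3, 10, so 2 × 7 = 14 readings.
- In neither class: dialysis-day home readings on Days 4, 6, 8, so 3 × 7 = 21 of 9 × 7 = 63 readings.

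**Session dialysed but not sampled.** No label changes. At 10–12 samples a session, in-session pairs fall from 30–36 to 20–24 per subject.

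**Session skipped.** The same pairs are lost, and labels change:

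| Skipped | That day becomes | Later non-dialysis days | Nominal +1 readings displaced | Nominal +2 readings displaced | Readings beyond +2 |
|---|---|---|---|---|---|
| Day 4 | +3 | Day 5: +1 to +4 | 7 of 28 | 0 of 14 | 14 |
| Day 6 | +2 | Day 7: +1 to +3 | 7 of 28 | 0 of 14 | 7 |
| Day 8 | +2 | Day 9: +1 to +3; Day 10: +2 to +4 | 7 of 28 | 7 of 14 | 14 |

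**Cohort share under schedule labelling.** There are 30 × 28 = 840 nominal +1 readings, so k skippers displace 7k/840: 0.8% for one, 2.5% for three, 5.0% for six. The documents give no skip rate. If a share p of subjects skips one session, each session being equally likely, the displaced shares are p/4 of the +1 days and p/6 of the +2 days. For p from 5% to 40% (assumed) these are 1.25% to 10% and 0.8% to 6.7%.

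**Effect on MARD.** The shift in pooled +1 MARD is the displaced share times the difference in MARD between displaced and true +1 readings. The documents give no such difference; I assume 2 to 10 percentage points.

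- Three skippers: 0.025 × 2 to 10 = 0.05 to 0.25 points.
- Six skippers: 0.05 × 2 to 10 = 0.1 to 0.5 points.
- At p = 40%: 0.10 × 2 to 10 = 0.2 to 1.0 points.

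**Does the text lead to schedule labelling?** No. The classes in Statistical Considerations, item 2, are counted from an HD day and described as lying between sessions. A scheduled day on which no dialysis took place is not naturally an HD day. The schedule tables carry no volume-state labels. On the plain reading, the displaced +1 readings drop out of that class and do not contaminate it.

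**Can a skip be recognised?** Yes. Study Procedures records dialysis run information. Statistical Considerations, item 5, lists duration of HD, volume removed and daily weight. The i-STAT results go on the flowsheet, so a dialysed session without samples shows a run record and no glucose values, while a skipped one shows neither.

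**The case for a change.** The best argument for a change is that it would be nearly free. A few sentences could define a missed session and tie volume state to the last dialysis performed, which would remove a choice otherwise made after the data are seen. Subjects are their own controls, so the within-subject share (25% of the +1 readings, and half of the +2 readings after a Day 8 skip) arguably matters more than 0.8% of the cohort. The two-session allowance also shows that some shortfall is expected.

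Part of this stands. The wording of the two rules does conflict for a subject who misses exactly one session, and no sentence states how to label days after a skip. The rest carries less weight:

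- The non-compliance label removes nobody from MARD, so the conflict has no effect on the analysis as written.
- Readings without a class are already normal here: 21 of 63 per subject have none when every session is kept. Another 7 to 14 in an occasional skipper is not a new kind of problem.
- The 50% figure for a Day 8 skip is doubtful as a misclassification. Day 10 would be called volume overloaded, the state the plan assigns to the longer interval.
- Inclusion/Exclusion Criteria, item 2, excludes patients who do not comply with HD therapies, which should make skips uncommon.

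**Conclusion.** The concern does not call for a change. The day counts are right, and so is the observation that the session rules sit badly together, but following the plan as written produces no wrong result. Blurring of the volume-state contrast needs schedule-day labelling, which the protocol nowhere prescribes and which its definition of the classes does not suggest. The data to separate a skipped session from an unsampled one are largely planned already, so the gap is one an analyst would fill by counting from the last dialysis performed.

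Even under schedule labelling, each skipper displaces 0.8% of the cohort's +1 readings. Six skippers would move pooled +1 MARD by 0.1 to 0.5 points under the assumed 2 to 10 point difference. That is small for a pilot with no stated test, threshold or power target for this contrast. The primary hypothesis compares non-dialysis days with dialysis and does not use the +1 and +2 labels.

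This rests on skips being few, on no make-up sessions, and on the assumed MARD difference. If skips were as common as the top of the assumed range (40% of subjects), schedule labelling could shift pooled +1 MARD by up to 1.0 point, but it would still require a labelling rule that the plan does not contain.
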